## ABBREVIATIONS AND DEFINITIONS OF TERMS

Abbreviation	Definition
API	Application Program Interface
BCT	Behavior Change Technique
BMI	Body Mass Index
DSMB	Data Safety Monitoring Board
DSM-IV-TR	Diagnostic and Statistical Manual of Mental Disorders
HEI	Healthy Eating Index
IMPACT	IMproving Physical Activity after Cancer Treatment
IRB	Institutional Review Board
MOST	Multiphase Optimization Strategy
MVPA	Moderate to Vigorous Physical Activity
PA	Physical Activity
NCI	National Cancer Institute
NIH	National Institutes of Health
OCT	Office of Clinical Trials
PAR-Q	Physical Activity Readiness Questionnaire
PAQ	Paffenbarger Physical Activity Questionnaire
REDCap	Research Electronic Data Capture
RCT	Randomized Clinical Trial
SCT	Social Cognitive Theory
SDT	Self-Determination Theory
SNAP	Studies of Novel Approaches to Prevention
TraCS	North Carolina Translational and Clinical Scices
YACS	Young Adult Cancer Survivor

## PROTOCOL SYNOPSIS

Study Title	A pilot randomized factorial trial to promote physical activity and healthy eating among young adult cancer survivors
Clinical Phase	NA
Study Rationale	Few studies have tested PA interventions specifically for YACS, and no studies have tested nutrition interventions among this population. To accelerate science in this area, we propose a pilot randomized factorial trial as part of the preparation phase of the Multiphase Optimization Strategy (MOST) framework to test the feasibility, acceptability, and effects of a digital PA and nutrition intervention designed specifically for YACS. Previous interventions have demonstrated the importance of self-regulation (i.e., self-monitoring of behaviors, small changes, goal setting and feedback) approaches to improve PA and nutrition behaviors among young adults and YACS. We aim to leverage our prior work to deliver a theory-based intervention using digital tools to simplify self-monitoring of PA, and dietary monitoring to provide tailored behavioral goals and messages to support increased physical activity and diet quality among YACS.
Study Objective(s)	
Primary
 

• To evaluate the feasibility of a theory-based, mobile PA and nutrition intervention, as characterized by the participation, accrual, and retention rates at 3-months.

 
Secondary
 

• To evaluate acceptability of the intervention as characterized by ratings of program acceptability and satisfaction at 3-months.

• To evaluate the adherence to the intervention as measured by daily self-monitoring of activity (Fitbit) and dietary tracking (Traffic Light Approach) from baseline to 3-months based on experimental conditions.

• To estimate the main effects of each of four intervention components on changes in behavioral measures (Fitbit measured MVPA and healthy eating index (HEI) using the NCI's 24-hour Recall (ASA-24)) at 3-months.

• To estimate the main effects of each of four intervention components on changes in secondary outcomes including anthropometric (weight), clinical (Fried physical phenotype using the FRAIL index) and psychosocial measures (health related quality of life) at 3 months.

Test Article(s) (If Applicable)	All participants will receive a core 3-month physical activity and healthy eating intervention that includes evidence-based lessons, behavioral skills training, and daily self-monitoring of physical activity and diet.

---

**Study Design**

The YACS HEAL (Young Adult Cancer Survivors Healthy Eating and Active Lifestyles) trial utilizes the Multiphase Optimization Strategy (MOST) framework and a 2 full factorial experimental trial to test the efficacy of 4 intervention components, to determine feasibility, acceptability, and effects of intervention components on physical activity (PA) and diet quality. Participants will receive a core 3-month digital PA and nutrition intervention delivered through a mobile app, with digital tools (PA tracker) and self-monitoring of behaviors. All participants will receive evidenced based lessons and behavioral skills training focused on PA and nutrition behavioral change, skills training, goal-setting, and weekly feedback on progress. Using the highly efficient, randomized factorial experimental design, we will test 4 intervention components--each with two levels:- 1) simplified dietary tracking based on the Traffic Light Approach (TLA, daily tracking of green (low-calorie, high nutrients) vs. red (high-calorie, high-fat, low nutrients) foods), 2) dietary goals using the TLA (daily green or red food goals vs. no goals), 3) supportive text messages (yes ( $\leq$  5 per week) vs. no), and 4) lesson delivery (all provided once vs. weekly).

---

**Subject Population****Inclusion Criteria**

1. Age  $\geq$ 18-39
2. Diagnosed with invasive cancer malignancy between the ages of 15-39 years
3. Diagnosed with invasive malignancy in the last 10 years of diagnosis, and with no evidence of progressive disease or second primary cancers
4. Completed active cancer directed therapy (cytotoxic chemotherapy, radiation therapy and/or definitive surgical intervention), except may be receiving “maintenance” therapy to prevent recurrences
5. No pre-existing medical conditions(s) that preclude adherence to an unsupervised exercise program including cardiovascular disease, congestive heart failure, pulmonary conditions, renal disease, and severe orthopedic conditions
6. Not currently meeting guideline recommendations of 150 MVPA minutes/week (self-report) and guideline recommendations for fruit and vegetable consumption
7. Have the ability to read, write and speak English
8. Own a smartphone with a data and text messaging plan
9. Willing to be randomized to any levels of the factors

**Exclusion Criteria**

1. History of heart attack or stroke within past 6 months
2. Untreated hypertension, hyperlipidemia, or diabetes, unless permission is provided by their health care provider.
3. Health problems which preclude ability to walk for PA
4. Report a heart condition, chest pain during periods of activity or rest, or loss of consciousness on the Physical Activity Readiness Questionnaire (PAR-Q; items 1-4).
5. Report a past diagnosis of or receiving treatment for a DSM-IV-TR eating disorder (anorexia nervosa or bulimia nervosa).
6. Currently pregnant, pregnant within the past 6 months, or planning to become pregnant within the next 6 months.
7. Hospitalization for depression or other psychiatric disorder within the past 12 months. History of psychotic disorder or bipolar disorder.
8. Plans for major surgery (e.g., breast reconstruction) during the study time

---

frame

9. Currently participating in a weight loss, nutrition or physical activity study or program or other study that would interfere with this study.
10. Currently using prescription weight loss medications

Number Of Subjects	72
Study Duration	Each subject's participation will last 4 months.
Study Phases	
Screening	(1) Screening : screening for eligibility and obtaining consent and (2) Baseline assessment
Study Treatment	(3) Intervention : study intervention/experimental treatment.
Follow-Up	(4) Follow-up assessment will occur at 6 weeks and 3 months
Efficacy Evaluations	NA
Pharmacokinetic Evaluations	NA
Safety Evaluations	All medical events and safety data will be assessed at assessment points or when interim events are reported by participants using a standard form used in our ongoing NIH funded trials.
Statistical And Analytic Plan	
The primary objective is to evaluate the feasibility and acceptability of a digital intervention components to increase PA and improve nutrition behaviors among YACS (n=80) at 3 months. Our primary feasibility measures are participation, accrual, and retention rates.
 
The secondary outcome analysis will use mixed effects models to test for differences in MVPA and HEI by intervention components across time (baseline, 6 weeks, and 3 months). Effects will be modeled as component x time interactions with the 3-month outcome as the primary endpoint.

DATA AND SAFETY MONITORING PLAN	
Data safety management in this trial is intended to achieve 4 objectives: 1) to minimize the occurrence of adverse effects, especially those related to intervention; 2) to effectively manage adverse events as they relate to the study; 3) to identify when the interventions should be suspended because of concerns for participant safety; and 4) to determine when interventions may be resumed after having been suspended. The Principal Investigator ([name]) will have primary responsibility for the safety of participants as it relates to the study protocol, which must be approved by the UNC IRB prior to study initiation. In addition, the North Carolina Translational and Clinical Sciences (TraCS) Institute Data Safety Monitoring Board (DSMB) is responsible for reviewing data from clinical trials approved by the UNC Biomedical IRB. Because the risks to subjects participating in this phase of this study are expected to be low, we do not anticipate the need for a formal Data Safety Monitoring Board. The research team will provide continuous monitoring of participant safety and periodic reporting to the IRB as required, including any Unanticipated Problems/Severe Adverse Events that may have occurred during the study. If risk or complexity is significant, the UNC Office of Human Research Ethics may require

Additional reporting or alternative data and safety monitoring. Data safety and monitoring activities continue until all participants have completed treatment and until all participants have been followed to the point at which study related adverse events would likely no longer be encountered.

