## 1.2 Name and Description of Investigational Intervention

The YACS HEAL (Young Adult Cancer Survivors Healthy Eating and Active Lifestyle) trial is a 2 full factorial experimental trial testing the efficacy of 4 intervention components (factors), each with two levels, to identify component levels that contribute to greater change in MVPA and diet quality among YACS. To do so, we will randomize 80 YAs with overweight or obesity to receive one level of each of the 4 intervention components, in addition to a core mobile-delivered behavioral physical activity and nutrition program.

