#### *Elements Common to All Experimental Conditions*

Core Intervention (n=80) all participants will receive a core intervention that includes PA and nutrition education modified from concepts of the Diabetes Prevention Program , our prior studies , and based around the consensus guideline recommendations for cancer survivors. Participants will be given digital tools to facilitate self-monitoring – a PA tracker and simplified diet tracking tool to support self-regulation of behaviors. The intervention will be delivered a mobile app integrated with Fitbit. Participants will receive an activity tracker (Fitbit) in the mail, followed by an introductory videochat session with an interventionist. In this session they will receive information relevant to their participation in the program, including an overview of how to use the study app (for both iOS and Android); Fitbit; the Traffic Light Log; how to self-monitor to achieve their daily goals (eating, activity, and self-weighing), and other information relevant to the conditions to which they have been randomized. Activity and dietary data are synced to study servers and activity is available in the app on pages that display participants' daily and overall progress towards their goals. The study app also includes 12 behavioral lessons that are delivered based on randomization. These include behavioral strategies with specific instruction on core cognitive and behavioral skills (i.e., goal setting, self-monitoring, problem solving, overcoming barriers, reaching out for social support, and cognitive restructuring).

Participants will receive qualitative feedback on self-monitoring behaviors and goal progress specific to MVPA and diet tracking (and goals). Feedback will include positive reinforcement and encouragement, strategies for barrier identification and overcoming barriers, and strategies for improving dietary and PA behaviors. Participants will receive tailored feedback summaries weekly. Participants will receive an email directing them to their feedback page. The feedback message will include feedback based on participants' number of days tracking diet and PA, and progress toward goals.

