## 4. STATISTICAL CONSIDERATIONS

### Sample Size and Power

The sample size is based on feasibility. Our primary feasibility measures are participation, accrual, and retention rates. Anticipated participation and retention rates are based on pilot feasibility studies among YACS and our previous work with this population. With an estimated participation rate of 85% (consistent with CO-I's experience, LCCC 1707), we anticipate it will be feasible to recruit 80 YACS within 6 months. We will test the null hypothesis that the proportion recruited is 50% or lower versus the alternative that it is 65% or greater using a one-tailed test at an alpha level of 0.05 with 95% power, which would support that the study is feasible.

We plan to accrue no more than 100 participants looking to have at least 80 evaluable participants, for 5 participants in each of the 16 groups. We expect accrual to take a total of 10 months at a rate of approximately 10 participants per month. We anticipate accruing 80 participants within 10 months, or 12-15 participants per month. A sample size of 80 achieves 99% power to detect a difference between a null hypothesis mean accrual rate of 12 participants/month and an alternative hypothesis mean of 15 participants/month with a significance level of 0.05 using a one-sided one-sample Poisson test.

For retention, we will test the null hypothesis that the retention is 70% or below versus the alternative that the retention is 90% or greater using a one-tailed test at a 0.05 alpha level. With 80 participants we would reject the null hypothesis that the retention is 70% if at least 62 participants are retained with 90% power, which would support that the study is feasible. With 80 participants we would reject the null hypothesis that the retention is 70% if at least 66 participants are retained with 97% power, which would support that the study is feasible.

All three endpoints must meet the proscribed criteria in order for the study to have successfully demonstrated feasibility.

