## 8. RECRUITMENT, CONSENT, AND RETENTION STRATEGY

### Recruitment

Based on previous trials among young adult cancer survivors (YACS), successful recruitment and timely enrollment of 62 YACS for the THRIVE trial (LCCC1709) and 280 YACS for IMPACT trial (LCCC1707, R01CA204965) our team has demonstrated the ability to recruit this population. Based on our previous experiences and estimates of YACS served by UNC, participants will be recruited on a rolling basis and randomized to 1 of 16 intervention conditions. We will use a multi-method recruitment strategy that demonstrated previous success to reach individuals across the United States, and include the following strategies:

- A) Direct mailings to individuals identified through the local UNC tumor registry. Used by [name] to recruit young adult cancer survivors (LCCC 1707, LCCC1709) and African American breast cancer survivors (LCCC1323), we will obtain a list of potentially eligible participants from the Carolina Data Warehouse for Health (CDW-H), which accesses UNC tumor registry data (i.e., participants from the UNC tumor registry are provided in a list from CDW-H). Potentially eligible survivors will be sent a letter of approach from the study PI, inviting them to participate and a study brochure describing the study and what it means to participate. The letters will invite interested individuals to visit a study

recruitment website or call research study staff to be screened by phone. We may follow up with up to two additional mailings if necessary.

- B) Local and national community-based programs. We will work with our AYA Oncology Program members, local programs and national community-based organizations dedicated to YACS with whom we have established relationship (e.g., Teen Cancer America, Ulman Foundation, Cervivor, Stupid Cancer, A Ballsy Sense of Tumor) to share and post recruitment information on various communication channels (e.g., Facebook, Instagram, Twitter, listservs, email). Unpaid Facebook posts by cancer organizations or friends was the primary approach used in our IMPACT study (LCCC 1707) to recruit 280 participants in 14 months.

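### The synopsis states 72 subjects where the plan is built on 80 (72/16 = 4.5 per cell), and the retention test at n = 80 carries two conflicting cut-offs, one of which exceeds its stated alpha

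*Combined protocol and SAP*

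**What the plan says.** **Sample size.** In the Protocol Synopsis, the row "Number Of Subjects" gives 72. Other places give 80:

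- Protocol Synopsis, Statistical And Analytic Plan: "improve nutrition behaviors among YACS (n=80) at 3 months".
- Section 1.2: "we will randomize 80 YAs with overweight or obesity".
- Section 2, Elements Common to All Experimental Conditions: "Core Intervention (n=80) all participants will receive a core intervention".
- Section 4, Sample Size and Power: "accrue no more than 100 participants looking to have at least 80 evaluable participants, for 5 participants in each of the 16 groups".

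The Recruitment section confirms the number of cells: participants are "randomized to 1 of 16 intervention conditions".

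**Retention.** Section 4 tests 70% or below against 90% or above, one-sided at 0.05. It then gives two rules in consecutive sentences, both for 80 participants. The first reads "With 80 participants we would reject the null hypothesis that the retention is 70% if at least 62 participants are retained", with a stated power of 90%. The second requires at least 66, with a stated power of 97%. Statistical Analysis in Section 4 defines the retention rate as those who completed the 3-month measures over those who consented. Section 4 also requires all three feasibility endpoints to pass before the study counts as feasible.

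**The concern.** A synopsis is where many readers take the enrolment target from, and here it disagrees with the section that justifies the sample size and with another row of the synopsis itself. Someone working to 72 would stop short of the planned number and could not fill the cells as described.

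The retention rule is a second, separate problem in the same part of the plan. It would exist even if the synopsis said 80. Two different pass marks for the same test at the same n cannot both be the rule, and one of them does not hold the stated alpha. Because all three endpoints must pass, the choice between the two marks can decide whether the pilot is declared feasible. As written, that choice could be made after the count is known.

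**Working it through.** **Inputs.** Synopsis N = 72; N = 80, 16 groups, 5 per group and an accrual cap of 100 from Section 4; retention p0 = 0.70, p1 = 0.90, one-sided alpha 0.05, cut-offs 62 and 66 from Section 4; denominator (number consented) from Statistical Analysis.

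**1. Cell arithmetic.** The plan's figure reproduces: 5 × 16 = 80. For the synopsis figure, 72/16 = 4.5, so equal cells are impossible. The nearest split is eight cells of 4 and eight of 5 (32 + 40 = 72).

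**2. Size of the shortfall.** (80 − 72)/80 = 10%. With outcome variance unchanged, a main-effect standard error scales with 1/√N, so the ratio is √(80/72) = 1.054, about 5% larger.

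**3. The two printed retention rules at n = 80.** For a rule of at least r retained, alpha = P(X ≥ r | n, 0.70) and power = P(X ≥ r | n, 0.90), with X binomial.

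| Rule | Exact alpha | Exact power | Stated alpha | Stated power |
|---|---|---|---|---|
| ≥ 62 of 80 | 0.087 | 99.97% | 0.05 | 90% |
| ≥ 66 of 80 | 0.008 | 98.8% | 0.05 | 97% |

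The 66 rule reproduces its stated power to within 2 points but uses far less than the allowed alpha. The 62 rule reproduces neither figure.

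**4. The cut-off implied by the stated alpha.** The requirement is the smallest r with P(X ≥ r | n, 0.70) ≤ 0.05.

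- n = 80: r = 63 gives 0.053 (fails); r = 64 gives 0.030, power 99.8%. The cut-off is 64/80.
- n = 100: r = 77 gives 0.076 (fails); r = 78 gives 0.048, power 99.99%. The cut-off is 78/100.

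A normal approximation at n = 80 gives 56 + 1.645 × √(80 × 0.7 × 0.3) = 56 + 1.645 × 4.099 = 62.74, so 63. With continuity correction it is 63.24, so 64. No version gives 62.

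**5. How often the printed rules would disagree.** They disagree when 62 to 65 of 80 are retained. The probability is P(X ≥ 62) − P(X ≥ 66):

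| True retention | P(X ≥ 62) | P(X ≥ 66) | Rules disagree |
|---|---|---|---|
| 70% | 0.087 | 0.008 | 0.079 |
| 80% | 0.762 | 0.346 | 0.416 |
| 85% | 0.974 | 0.787 | 0.187 |
| 90% | 0.9997 | 0.988 | 0.012 |

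**6. What N = 72 would do to a correct retention rule.** The exact cut-off is 58/72 (80.6%), alpha 0.030, power 99.5%, against 64/80 (80.0%), alpha 0.030, power 99.8%.

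**The case against.** The case for treating the 72 as minor is strong on consequences. Section 4 is the operative text, it clearly says 80, and no rule anywhere acts on 72, so an actual stop at 72 is unlikely. Cells of 4 and 5 still allow 36 participants at each level of every factor, the planned mixed models do not need equal cells, and attrition will unbalance the cells even at 80. The 5% loss of precision touches secondary outcomes only, in a study whose size rests on feasibility and whose limitations paragraph already says effect estimates may be inconclusive. All of this stands. It limits the harm but does not remove the contradiction.

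An innocent meaning for 72 is available: 0.90 × 80 = 72, which would be the expected completers at 90% retention. The documents do not say so, the row is labelled as the number of subjects, and Section 4 calls 80 the evaluable number.

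Some stronger readings are tempting but not supported:

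- **That the 62 rule was carried over from a 72-subject design.** A cut-off of 62 at n = 72 does have power 89.8%, close to the printed 90%. Its alpha, however, is 0.0012, and a 72-subject design at the stated 0.05 would give 58. At n = 80, 62 is also the smallest cut-off for a one-sided alpha of 0.10 (61 gives 0.135), which explains the count equally well though not the power. The text itself says 80. The origin cannot be established.
- **That 72 versus 80 alters the accrual and participation tests.** Accrual is a rate that depends on recruitment time, and participation is taken over eligible people. Neither is fixed directly by this number.
- **That 72 would change the retention decision materially.** As proportions the correct cut-offs are almost the same.

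**Conclusion.** Two corrections are warranted. First, 72 in the synopsis is inconsistent with every other statement of the trial's size and incompatible with 5 per cell. The shortfall would be 10%, with main-effect standard errors about 5% larger, and main effects would still be estimable. Second, and independently of the 72, the retention test has two incompatible cut-offs at n = 80. The 62 rule has alpha 0.087 against a stated 0.05, and the choice between 62 and 66 would change the feasibility conclusion with a probability of about 0.19 to 0.42 if true retention were 85% to 80%, but only about 0.01 at 90%.

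The cut-offs assume an exact binomial test. The plan specifies a one-sample test of proportions without saying exact or approximate; an uncorrected normal approximation would give 63, whose exact alpha is 0.053. They also assume a denominator of exactly 80 or 100. Since the plan divides by the number consented, the true denominator may lie between or differ from these.

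**What to change.** 1. In the synopsis, replace 72 with the planned 80 evaluable participants, 5 per cell, at most 100 accrued. State whether the row means accrued, randomized or evaluable, and use the same term in Sections 1.2, 2 and 4, because Section 1.2 speaks of randomizing 80 while Section 4 speaks of 80 evaluable.
2. In Section 4, remove the 62 rule, on the ground that it exceeds the stated alpha.
3. State one retention cut-off, name the test as exact binomial, and tie it to the number consented. With one-sided alpha 0.05 this is 64 of 80, or 78 of 100 if 100 consent. Since the final denominator is not known in advance, write the rule as the smallest count with an exact upper-tail probability of at most 0.05 under 70%, and give these two values as examples. If the sponsor prefers the stricter 66 of 80, it should be stated as a deliberate choice with its own alpha (0.008) and power (98.8%).

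The cost is one corrected synopsis entry and one rewritten paragraph. It needs no participants, visits or data beyond those already planned, but the rule should be fixed before the 3-month retention count is known.
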